**Protocol:**

Following the consent process the participants will be asked to participate in the following:

1. Participants will complete Central Sensitization Inventory (CSI) and the Columbia Suicide Severity Rating (CSSR) as well as any necessary labs. These will be done in person at the time of consent/enrollment. If the participant answers Yes on any of the CSSR questions, they will exit the study. If any participant scores < 40 on the CSI, they will exit the study.
2. If they still qualify for the study, they will complete (1) the Baseline Subject Demographic form, (2) the Pain, Enjoyment of Life and General Activity form (PEG-3), and (3) the Knee Injury and Osteoarthritis Outcomes Score (KOOS). These will be done in person at the pre-op visit.

3. All participants will meet with a physical therapist prior to surgery to assess baseline functional levels using established assessment surveys. The approximate time to complete these assessments is 30 minutes.

The surveys used include: Timed Up and Go (TUG)

Stand-Up, Sit-Down (STS)

Patient-Specific Functional Scale Assessment (PSFS)

3. Participants are randomized at the pre-op visit to standard of care vs study treatment arm using a computer-generated block randomization sequence. The allocation of concealment will be ensured using a sealed envelope technique.

4. If the participant is not randomized to the study medication arm, they will proceed with usual peri-operative management.

5. If the participant is randomized to study medication arm, they will be directed to the UIHC Discharge Pharmacy to retrieve the study drug. Additionally, they will be provided information about the medication, possible side effects and dosing schedule.

**Dosing Schedule**

Pre-surgery (days 1-7) pregabalin 75mg twice daily

Post-surgery (days 1-7) pregabalin 150mg twice daily, then (days 8-14) pregabalin 75mg twice daily

6. Day of Surgery (DOS): Someone from the research team will meet with all participants in DOSA to (1) answer any questions about continued participation in the study. For those participants in the study medication arm, the research team member will also evaluate if they have (2) completed the study medication schedule, (3) determine if they have noticed any side effects from the medication (including the CSSR scale), and (4) remind the participant of post-surgical medication dosing schedule. If the participant did not tolerate the study medication they will exit the study and continue to receive standard surgical care. If the patient answers Yes to any of the CSSR items, they will be advised to seek out behavioral healthcare. If they answer Yes to questions 4,5, or 6, they will be immediately taken to the ED by study team member for evaluation. They will stop the study medication and exit the study at that time. Proceeding with surgery will be deferred to the primary surgery team. This visit is expected to take less than 15 minutes.

7. All participants undergo a post-operative Physical Therapy assessment, which normally

occurs within a week of surgery per standard of care. At that time, the functional levels as outlined above including TUG, STS, and PSFS will be re-evaluated. The approximate time spent is 30 minutes.

8. All participants will be contacted by the study pharmacist about 7 days after surgery by telephone. The pharmacist will also determine the amount of other pain medications that have been needed for pain relief for all participants. The goal of this assessment is to determine how the participant is faring with the study medication (if randomized to the study medication arm) and other pain medications. The pharmacist will review the study medication dosing schedule with these participants and re-assess with the CSSR scale. If the participant did not tolerate the study medication they will exit the study and continue to receive standard post-surgical care. If the patient answers Yes to any of the CSSR items, they will be advised to seek out behavioral healthcare. If they answer Yes to questions 4,5, or 6, they will be advised to seek immediate medical attention or local EMS will be contacted by the pharmacist. They will stop the study medication and exit the study at that time.

9. Patients will have a 6-week post-operative visit with their surgical team and research study team. At this time, all participants will again complete the Knee Injury and Osteoarthritis Outcomes Score (KOOS), the PEG-3 pain survey, and the Central Sensitization Inventory (CSI) assessments. Also the participant will be asked to report how much opioid medication (if any) they are taking and the physical therapist will repeat the functional tests (TUG, STS, PSFS). The time to complete these evaluations is approximately 60 minutes.

10. This will complete the study participation.

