#### Analysis/Statistical Plan:

Treatment-stratified summary statistics will be calculated for all baseline measures, including demographics and clinical outcomes. Categorical measures will be presented as counts and percentages. Continuous measures will be assessed for normality and presented as either means and standard deviations or medians and interquartile ranges. Assessments of between-group differences will be conducted for all baseline non-subscale measures using Fisher's exact, two-sample t-, or Wilcoxon rank sum tests. Between-group differences for baseline subscale measures (following a 5-point Likert scale) will be assessed using cumulative logistic regression to utilize the ordinality of the measure.

Between-group changes (baseline to week 6) in the primary outcome (KOOS- ADL) and secondary outcomes (KOOS subscale scores (pain, symptoms, sports/recreation, and quality of life subscales, pain scores, differences Timed Up and Go Test (TUG), the Sit-to-Stand Test (STS) and the Patient Specific Functional Scale (PSFS) will be assessed by calculating the within-subject differences. Distributions for each outcome's 6-week change will be examined. Measures with normally distributed differences will follow the two-sample t-test to compare changes between treatment groups, and measures with non-normally distributed differences will follow the Wilcoxon rank sum test. Tests with p-values < 0.05 will be considered statistically significant.

As an exploratory outcome, we will investigate the relationship between 6-week changes in CSI scores and changes in pain and function outcomes. Associations between normally and non-normally distributed measures will be investigated using Pearson's and Spearman's correlations, respectively.

Adverse effects will be calculated for each treatment group and presented counts and percentages.

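### Intolerance of pregabalin after randomisation leads to study exit, which can happen in one arm only, and the plan does not say that those who exit are followed or analysed as randomised

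*Combined protocol and SAP*

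**What the plan says.** The Protocol section fixes the order of events: "Participants are randomized at the pre-op visit to standard of care vs study treatment arm". For controls, "If the participant is not randomized to the study medication arm, they will proceed with usual peri-operative management"; no placebo is described.

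Tolerance of the study drug is checked twice after that. Step 6, on the day of surgery, says "If the participant did not tolerate the study medication they will exit the study and continue to receive standard surgical care". Step 8, the pharmacist call about 7 days after surgery, says "If the participant did not tolerate the study medication they will exit the study and continue to receive standard post-surgical care".

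Two other steps are written for everyone. Step 7 says "All participants undergo a post-operative Physical Therapy assessment", and step 9 says that at 6 weeks "all participants will again complete the Knee Injury and Osteoarthritis Outcomes Score".

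In the Analysis/Statistical Plan, changes from baseline to week 6 in KOOS-ADL (primary) and in the secondary outcomes "will be assessed by calculating the within-subject differences", then compared by t-test or Wilcoxon rank sum test. That section names no analysis population, no rule for missing week-6 values and no sensitivity analysis.

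**The concern.** The exit rule acts after randomisation, and only in the arm that receives study drug. If exit ends data collection, the pregabalin arm loses participants for a reason caused by treatment, while the comparable people in the control arm stay in. The primary and secondary comparisons would then set pregabalin participants who tolerated the drug against all controls, which is not the comparison that randomisation protects. A within-subject change needs a week-6 value, so a participant without one leaves the comparison without any further decision being taken.

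**Working it through.** **What exit means in this protocol**

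- Step 1 uses the same expression for people who fail the CSSR or CSI screen. Step 2 continues only with those who still qualify, so there exit means no further assessments. That step precedes randomisation; it shows how the term is used and is not a second defect.
- Steps 6 and 8 send intolerant participants to standard care and mention no study follow-up.
- Steps 7 and 9 address all participants and do not say whether someone who has exited still counts as one.

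The usage in step 1 favours the reading that exiters give no week-6 data. The wording of steps 7 and 9 allows the other reading. The two sets of steps cannot both be followed as written.

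**Size of the bias if exiters are lost**

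The plan gives no figure to reproduce: the available text has no sample size, SD, allocation ratio or exit rate. All inputs below are assumptions: no true drug effect, equal arms of 30, 50 or 100 randomised, a t-test at two-sided 0.05 (the plan does not state sidedness), and SD 1 within exiters and within non-exiters.

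Let *p* be the fraction who would exit on pregabalin, and *d* the amount, in SD of the 6-week change, by which their mean falls below that of non-exiters, μ. The control arm keeps its counterparts of the exiters, so its mean is μ − *pd*. The pregabalin arm retains only non-exiters, so its mean is μ. Hence

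bias = *p* × *d*.

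If a fraction *r* of exiters is followed and analysed in the assigned arm,

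residual bias = *pd*(1 − *p*)(1 − *r*) / (1 − *p*(1 − *r*)).

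For *p* = 0.2, *d* = 0.5 and *r* = 0.8 this is 0.10 × 0.8 × 0.2 / 0.96 = 0.017 SD.

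Simulation with 60,000 trials per scenario gives:

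| Exits *p* | *d* (SD) | Exiters followed | Bias (SD) | Type I error at 30 / 50 / 100 per arm |
|---|---|---|---|---|
| 10% | 0.3 | none | 0.03 | 5.0 / 5.1 / 5.6% |
| 20% | 0.5 | none | 0.10 | 6.4 / 7.4 / 10.0% |
| 20% | −0.5 | none | −0.10 | 6.3 / 7.2 / 10.0% |
| 20% | 0 | none | 0 | 4.9 / 5.0 / 5.0% |
| 20% | 0.5 | 80% | 0.017 | 5.0 / 5.2 / 5.2% |

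Check by normal approximation for *p* = 0.2, *d* = 0.5, 50 per arm, none followed: SE = √[(1 + 0.2 × 0.8 × 0.25)/50 + 1/(50 × 0.8)] = √0.0458 = 0.214, so the shift is 0.10/0.214 = 0.467 standard errors and the rejection rate is 7.5%. At 30 and 100 per arm the same formula gives 6.5% and 10.1%.

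**Why imputation alone would not repair it**

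Imputing from arm and baseline measures, without exit status, fills in exiters as if they were pregabalin stayers. If baseline does not predict the difference, they are placed at μ and the bias stays at *pd*. A shift *s* applied to a missing fraction *m* of the pregabalin arm moves the estimate by *m* × *s*. A range of −0.5 to +0.5 SD therefore moves it by ±0.10 SD when all of 20% exiters are missing, and by ±0.02 SD when 80% of them are followed (*m* = 0.2 × 0.2 = 4%).

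**The case against.** The best reply is that the protocol never says exiters' outcomes go uncollected. The intolerance sentences speak only of leaving the study and returning to standard care, while the post-operative and 6-week assessments are described for everyone. This stands to the extent that loss of week-6 data is an inference, not a stated rule. It does not remove the contradiction: staff could follow either wording, and the analysis section names no population that would settle the matter.

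A reader might infer from "They will stop the study medication and exit the study at that time" that stopping the drug and exiting are two separate acts, and so that exit must end follow-up. That sentence belongs to the CSSR rule, not the intolerance rule, and should not carry the argument. The usage in step 1 is the better evidence.

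It can also be said that the plan is not blind to the problem. Adverse effects are to be reported by arm, and participants who exit at the day-7 call may already have had the early TUG, STS and PSFS tests. This is partial information on who exits, but it does not replace their week-6 KOOS-ADL.

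Finally, the size rests wholly on assumed inputs, and one plausible set gives almost no effect. That is correct. The case for change rests on the one-sided exit rule, not on any of the illustrative error rates.

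**Conclusion.** The point holds in this form: a written rule, applied after randomisation and able to act in one arm only, would on its natural reading remove participants from the primary comparison for a treatment-related reason. It also conflicts with the steps written for all participants.

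A reader might infer that the rule will favour pregabalin. The documents do not support a direction: the bias favours pregabalin if exiters would have recovered less well, goes against it if better, and is nil if they do not differ. Nor do they support a particular size. The range shown, from negligible to 0.10 SD in either direction with type I error up to about 10%, depends on the assumed exit rate, difference and arm size, and on a t-test; the Wilcoxon alternative was not simulated.

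The finding is limited to the available text: one part of the document and the consent pages could not be read. If follow-up of exiters is provided for there, steps 6 and 8 still need to agree with it. The matter should be settled while week-6 data can still be collected, because values not collected then cannot be recovered.

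**What to change.** 1. In the intolerance sentences of steps 6 and 8, separate stopping the drug from leaving data collection. Suggested text: *Participants who stop study medication because of intolerance are still asked for the scheduled post-operative and week-6 assessments unless they withdraw consent.* Leave the rules on stopping medication and on safety referral unchanged. The CSSR exit is also assessed after randomisation in the drug arm; the sponsor should reconcile it with steps 7 and 9.
2. In the Analysis/Statistical Plan add: *The primary KOOS-ADL comparison includes all randomised participants in their assigned arm, regardless of adherence.*
3. For exiters whose week-6 value is still missing, pre-specify a sensitivity analysis that shifts those pregabalin-arm values over a stated range in both directions. The ±0.5 SD used above is only an example. Imputation from arm and baseline alone is not enough.
4. Report exits by arm, time and reason.

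The cost is a wording change, possibly with a consent and ethics update, a short analysis paragraph, and follow-up of those who stop the drug at visits that already exist. The effect estimate may be diluted by participants who stopped early.

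### Adverse effects are reported by arm, but the listed post-randomization safety questions go mainly to the study medication arm and stop at about day 7, while dosing runs to day 14

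*Combined protocol and SAP*

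**What the plan says.** The last sentence of the Analysis/Statistical Plan has adverse effects summarized as counts and percentages in each arm. It gives no definition, collection method or time window.

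The CSSR at enrollment (step 1) is for everyone, but it precedes randomization. The later contacts are these:

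- **Step 6, day of surgery.** The research team meets every participant, but the safety items are restricted: "For those participants in the study medication arm, the research team member will also evaluate if they have (2) completed the study medication schedule". The next item in that list is to "determine if they have noticed any side effects from the medication (including the CSSR scale").
- **Step 7, post-operative physical therapy.** Only TUG, STS and PSFS are listed.
- **Step 8, pharmacist call at about day 7.** Everyone is called. The stated goal is to learn "how the participant is faring with the study medication (if randomized to the study medication arm) and other pain medications". Then: "The pharmacist will review the study medication dosing schedule with these participants and re-assess with the CSSR scale".
- **Step 9, 6-week visit.** Here "all participants will again complete the Knee Injury and Osteoarthritis Outcomes Score (KOOS), the PEG-3 pain survey, and the Central Sensitization Inventory (CSI) assessments". Opioid use and the three functional tests are added. Neither the CSSR nor a side-effect question is listed, and step 10 then ends participation.

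The Dosing Schedule continues past the call: "Post-surgery (days 1-7) pregabalin 150mg twice daily, then (days 8-14) pregabalin 75mg twice daily".

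**The concern.** A by-arm adverse-effect table can be read across only if both arms were asked similar things at similar times. Followed as written, the listed procedures put events that were asked about in the medication arm beside events that were mostly volunteered in the control arm. A difference in percentages could then reflect who was asked as well as what the drug did, and no analysis can repair that after data collection.

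There is also a safety aspect. The protocol takes suicidality seriously: it screens at entry, repeats the CSSR, and sets emergency actions for a Yes to questions 4, 5 or 6. The listed checks nevertheless end while participants are still taking pregabalin, and none covers the period after it is stopped.

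**Working it through.** The plan gives no figure to reproduce. The documents state no sample size and no expected adverse-effect rate, so the distortion in the percentages cannot be calculated. What can be checked is who is asked, and how much exposure follows the last question.

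**Who is asked after randomization** (protocol steps 6 to 9)

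| Contact | Reaches | Medication arm | Control arm |
|---|---|---|---|
| Step 6, day of surgery | both arms | side effects and CSSR | neither |
| Step 7, physical therapy | both arms | neither | neither |
| Step 8, call at about day 7 | both arms | study-drug experience and CSSR | other pain medications; CSSR unclear |
| Step 9, week 6 | both arms | neither | neither |

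The medication arm has 2 contacts with a side-effect or tolerability question and the CSSR. In step 8, the people whose CSSR is repeated are those whose study dosing schedule is reviewed. Controls have no such schedule, so the natural reading is the medication arm only, which gives controls 0. On the broadest reading controls have 1 CSSR. On either reading they have no clearly listed side-effect question.

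**Scheduled dose** (Dosing Schedule)

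- Pre-surgery, 7 days: 7 × (2 × 75) = 1,050 mg
- Post-surgery days 1–7: 7 × (2 × 150) = 2,100 mg
- Post-surgery days 8–14: 7 × (2 × 75) = 1,050 mg
- Total: 21 days and 4,200 mg

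**Exposure after the last listed check.** The call day is counted as dosed before the call. Step 8 gives no window around day 7, so days 5 and 9 are my assumption to show the range.

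| Call on | Dosing days left | Share of days | Dose left | Share of dose |
|---|---|---|---|---|
| day 5 | 9 | 9/21 = 43% | 2 × 300 + 7 × 150 = 1,650 mg | 1,650/4,200 = 39% |
| day 7 | 7 | 7/21 = 33% | 7 × 150 = 1,050 mg | 1,050/4,200 = 25% |
| day 9 | 5 | 5/21 = 24% | 5 × 150 = 750 mg | 750/4,200 = 18% |

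**Follow-up after the last listed check.** Taking week 6 as day 42, 42 − 7 = 35 of 42 post-operative days (83%) follow a day-7 call. Of these, 42 − 14 = 28 days are after the last scheduled dose.

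**The case against.** Several points on the other side have weight.

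- **No test is planned.** The adverse-effect summary is descriptive. That stands, but readers will compare two percentages set side by side. A footnote on the collection method would warn them; it would not supply the missing answers.
- **Arm-specific questions have a rationale.** Controls receive usual care and no placebo is described, so asking them about effects of the study drug makes little sense. If the table means drug effects only, a parallel question is unnecessary. But then a control-arm percentage has little meaning, and the plan asks for one.
- **The heaviest exposure is checked.** With a day-7 call, both the pre-surgery week and the 300 mg/day week come before it. What remains is a step-down at a daily dose already taken before surgery. This limits the seriousness of the timing gap without closing it.

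A reader might infer that controls are never asked anything about safety, a clean 2 against 0. The documents do not support that: the call reaches everyone, how participants fare with other pain medications may draw out some control events, and the CSSR wording is ambiguous. A reader might also infer that events after day 7 would be recorded only if the participant raised them. That is too strong, because step 9 is an in-person visit with the surgical and research teams, and failing to list a question is not a statement that nothing is recorded.

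**Conclusion.** The point holds in a limited form. The listed post-randomization safety questions are for the medication arm at step 6 and mainly for that arm at step 8, and none is listed for either arm afterwards. With a day-7 call, the last check leaves 33% of dosing days and 25% of the scheduled dose uncovered; the assumed day 5 to day 9 window gives 24–43% and 18–39%. The by-arm percentages could therefore differ because of collection. The documents do not show that they will, or by how much.

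This rests on the procedures as listed. A general adverse-event procedure in text not provided cannot be excluded. The KOOS-ADL analysis is not affected. I would place the point between a change that should be made and one to consider, with moderate confidence.

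**What to change.** **Collection.** At the three existing contacts that carry or could carry safety questions and already reach both arms (step 6, step 8 and step 9), ask everyone the CSSR and one identically worded side-effect or new-symptom question, each covering the time since the previous contact. Keep the existing referral actions: those of step 8 for the telephone call, and those of step 6 for the in-person visits, including "If they answer Yes to questions 4,5, or 6, they will be immediately taken to the ED by study team member for evaluation".

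**Table.** Count events from all three contacts for all randomized participants by assigned arm, including those who stop the drug or exit at step 6 or 8. Show events by contact or onset period, and state how many in each arm were asked at each contact.

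The comparison should not rest on the week-6 answers alone. Under step 8, "If the participant did not tolerate the study medication they will exit the study and continue to receive standard post-surgical care", and step 6 has a matching rule. Only the medication arm can leave for that reason, so a week-6-only comparison could lose some of the worst drug reactions from one arm and make pregabalin look safer than it is.

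**Cost.** Protocol and table wording, and a few more minutes per contact. Recall at the 6-week visit would span about 5 weeks (35 days), and a question asked then cannot stop dosing. A call to both arms near day 14 would shorten recall and allow earlier referral, but it is a new contact and optional.

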#### Analysis/Statistical Plan:

Treatment-stratified summary statistics will be calculated for all baseline measures, including demographics and clinical outcomes. Categorical measures will be presented as counts and percentages. Continuous measures will be assessed for normality and presented as either means and standard deviations or medians and interquartile ranges. Assessments of between-group differences will be conducted for all baseline non-subscale measures using Fisher's exact, two-sample t-, or Wilcoxon rank sum tests. Between-group differences for baseline subscale measures (following a 5-point Likert scale) will be assessed using cumulative logistic regression to utilize the ordinality of the measure.

Between-group changes (baseline to week 6) in the primary outcome (KOOS- ADL) and secondary outcomes (KOOS subscale scores (pain, symptoms, sports/recreation, and quality of life subscales, pain scores, differences Timed Up and Go Test (TUG), the Sit-to-Stand Test (STS) and the Patient Specific Functional Scale (PSFS) will be assessed by calculating the within-subject differences. Distributions for each outcome's 6-week change will be examined. Measures with normally distributed differences will follow the two-sample t-test to compare changes between treatment groups, and measures with non-normally distributed differences will follow the Wilcoxon rank sum test. Tests with p-values < 0.05 will be considered statistically significant.

As an exploratory outcome, we will investigate the relationship between 6-week changes in CSI scores and changes in pain and function outcomes. Associations between normally and non-normally distributed measures will be investigated using Pearson's and Spearman's correlations, respectively.

Adverse effects will be calculated for each treatment group and presented counts and percentages.

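### Cheap improvement, not an error: the primary KOOS-ADL comparison uses raw change, leaves the choice of test until the data are seen, and names no effect estimate or confidence interval; one prespecified baseline-adjusted analysis would settle this.

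*Combined protocol and SAP*

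**What the plan says.** The Analysis/Statistical Plan defines the primary comparison as "Between-group changes (baseline to week 6) in the primary outcome (KOOS- ADL") and says that it "will be assessed by calculating the within-subject differences". The distribution of each outcome's "6-week change will be examined", and the test follows from what is seen: "Measures with normally distributed differences will follow the two-sample t-test to compare changes between treatment groups", while "measures with non-normally distributed differences will follow the Wilcoxon rank sum test". The only decision rule is "Tests with p-values < 0.05 will be considered statistically significant".

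The section gives no normality test, threshold or graphical rule. It does not adjust the comparison for baseline, and it names no mean difference, location shift or confidence interval for the primary outcome. Nothing elsewhere in the document supplies these.

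The data for a baseline-adjusted analysis are already planned. Step 2 of the Protocol section lists "the Knee Injury and Osteoarthritis Outcomes Score (KOOS). These will be done in person at the pre-op visit", and step 9 (under Dosing Schedule) says that at the 6-week visit "all participants will again complete the Knee Injury and Osteoarthritis Outcomes Score (KOOS").

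**The concern.** Three features of one short paragraph combine.

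- **Baseline handling.** Analysing raw change fixes the coefficient of baseline at 1, in the Wilcoxon branch as well as the t-test branch. Estimating that coefficient is never less precise in large samples and is often more precise. It also deals with chance baseline imbalance, but this is part of the same gain and not a second one.
- **Choice of test.** The test is chosen after the changes have been looked at, by an unstated standard. Two analysts who both follow the plan can report different primary tests from the same data.
- **Reported quantity.** The plan promises a p-value. Whether the primary effect will be a difference in means or a rank comparison is not settled, and no interval is promised in either case. A reader may be left without an effect in KOOS points to weigh.

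**Working it through.** **Inputs.** From the documents: KOOS-ADL at baseline and week 6, two randomized arms, raw change as the analysed quantity, alpha 0.05 (sidedness not stated; two-sided assumed). The available text gives no sample size, SD, correlation or skew, so there is no stated figure to reproduce. Assumed: ρ, the baseline to week-6 correlation, of 0.3, 0.5 or 0.7; k, baseline SD divided by week-6 SD, of 0.7 or 1, with 1.25 as a check.

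**Step 1: large-sample variance.** Set the week-6 SD to 1. Per participant:

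- change score: 1 + k² − 2ρk
- ANCOVA: 1 − ρ²
- difference: (1 + k² − 2ρk) − (1 − ρ²) = (k − ρ)², which is never negative and is zero when ρ = k, that is, when the true slope ρ/k is 1.

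Example, k = 1 and ρ = 0.5: 0.75 / 1.00 = 0.75. Example, k = 0.7 and ρ = 0.3: 0.91 / 1.07 = 0.85.

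| ANCOVA variance / change-score variance | ρ = 0.3 | ρ = 0.5 | ρ = 0.7 |
|---|---|---|---|
| k = 0.7 | 0.85 | 0.95 | 1.00 |
| k = 1 | 0.65 | 0.75 | 0.85 |
| k = 1.25 | 0.50 | 0.57 | 0.63 |

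If the t-test on change has 80% power, ANCOVA with the same participants has power Φ[(1.96 + 0.842)/√ratio − 1.96]. At k = 1 this is 93.5%, 89.9% and 86.0%.

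**Step 2: against the procedure actually planned.** The plan can switch to Wilcoxon, which does better than the t-test when errors are skewed, so Step 1 is not the whole comparison. Simulation: 30 per arm, 10,000 trials per cell, normal baseline, effect set for 80% power of the t-test on change. The planned procedure was represented by Shapiro-Wilk at 0.05 on within-arm-centred changes; this rule is an assumption, because the plan has none. ANCOVA used HC2 standard errors and t on N − 3 degrees of freedom. Entries are planned power → ANCOVA power.

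| Errors | k | ρ = 0.3 | ρ = 0.5 | ρ = 0.7 |
|---|---|---|---|---|
| Normal | 1 | .801 → .931 | .794 → .890 | .800 → .857 |
| Normal | 0.7 | .801 → .855 | .800 → .813 | .803 → .794 |
| Moderate skew (gamma, skewness 1) | 1 | .816 → .926 | .822 → .889 | .829 → .854 |
| Moderate skew | 0.7 | .829 → .853 | .836 → .813 | .849 → .798 |
| Exponential (skewness 2) | 1 | .855 → .917 | .878 → .886 | .910 → .847 |
| Exponential | 0.7 | .911 → .853 | .941 → .816 | .952 → .792 |

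By subtraction, ANCOVA changes power by about −1 to +13 points with normal errors, −5 to +11 with moderate skew and −16 to +6 with exponential errors. At k = 1.25 it gained about 7 to 18 points in all nine cells.

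The losses do not follow the baseline slope alone. Moderate skew with k = 1 and ρ = 0.7 has slope 0.70 and gains 2.5 points. Exponential errors with k = 0.7 and ρ = 0.3 have slope 0.3/0.7 = 0.43 and lose about 6.

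**Step 3: how open the choice of test is.** Under the assumed rule at 30 per arm, Wilcoxon becomes the primary test in about 5% of trials with normal errors and 27% to 75% with moderate skew. In the same powered trials (k of 0.7 and 1), the two tests give different verdicts at 0.05 in about 6% (normal), 6% to 8% (moderate skew) and 8% to 16% (exponential).

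**Step 4: type I error.** Over the null settings with 20, 30 and 50 per arm, the planned procedure rejected in 4.6% to 5.6% of trials and ANCOVA in 4.4% to 5.4%. Always taking the smaller of the two p-values, the most that an unstated criterion could allow, gave 5.6% to 7.2%.

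**The case against.** A t-test or rank sum test on change is an accepted analysis of a randomized trial. A reader might infer from the concern that the planned analysis is biased or inflates false positives. The documents do not support that: randomization makes the change-score estimate unbiased, and Step 4 shows rejection rates close to 5%. Even the worst use of the open choice of test adds about two points, and nothing in the plan says that it would be used that way.

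A second tempting inference is that ANCOVA must have more power in this trial. That is not supported either. In 7 of the 18 cells tabulated it falls below the planned procedure, and the documents give nothing that says which cell applies.

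A third is that a Wilcoxon result cannot be expressed in KOOS points. The test alone gives no such figure, but the Hodges-Lehmann shift and its interval do; the plan simply does not ask for them. The reporting gap can therefore be closed without ANCOVA.

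All three points stand, and they limit the claim. They do not answer what remains: the primary effect measure is not fixed, no estimate or interval is promised, and baseline information that is already collected is used only with its coefficient set to 1.

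**Conclusion.** The point holds as a low-cost improvement. The planned tests are sound; the loss is in precision and in having a primary effect measure settled before the data are seen. The second part follows from the text alone. The first depends on assumptions: relative to the t-test on change, the variance saving runs from 35% (k = 1, ρ = 0.3) to nothing (k = 0.7, ρ = 0.7), and is larger when baseline varies more than week 6.

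Relative to the planned t-or-Wilcoxon procedure, the saving can turn into a loss. At 30 per arm this happens with moderate skew at k = 0.7 and ρ of 0.5 or more, and with exponential errors at k = 0.7 for every ρ and at k = 1 with ρ = 0.7. With normal errors the only loss is about 1 point, at k = 0.7 and ρ = 0.7. The comparison rests on an assumed normality rule and an assumed sample size. The lack of a stated criterion for normality is, on its own, a missing detail with a small effect on error rates.

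**What to change.** Before any outcome data are examined, state in the Analysis/Statistical Plan:

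- **Primary analysis:** linear regression of week-6 KOOS-ADL on randomized arm and baseline KOOS-ADL, reporting the adjusted mean difference with 95% CI and a two-sided p-value. Fix one standard-error method whatever the residuals look like, for example HC2 with t critical values on N − 3 degrees of freedom.
- **Sensitivity analysis:** Wilcoxon on the change score, with the Hodges-Lehmann shift and its CI.
- **Secondary outcomes:** the same regression for the other KOOS subscales, each with its own baseline. For TUG, STS and PSFS it is optional, because the documents give no distributional information to support it.

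If the team expects strongly skewed changes and does not want to risk power, the minimum alternative is one named primary test on change with a matching estimate and 95% CI: the mean difference for the t-test, or the Hodges-Lehmann shift for Wilcoxon. This closes the prespecification gap without relying on any assumed correlation.

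The cost is wording, one degree of freedom, and possible power loss when errors are skewed and either baseline varies less than the week-6 score or the correlation is high. No new data are needed. How participants who exit the study (steps 6 and 8) are analysed is a separate issue that this change does not settle.
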